Baseline demographic and clinical data will be described between treatment and placebo study arms as mean \pm standard deviation for continuous variables and compared using Student's T-test. Whereas discrete variables will be represented as a number and (%) and compared using the χ^2 or Fisher's exact test, as appropriate.

The time course of continuous variables will be presented using standard descriptive summary statistics calculated at each scheduled measuring time point and the last individual measuring time point. Moreover, standard descriptive summary statistics will be calculated for the change (absolute or percent) from baseline to each scheduled measuring time point after baseline and the last individual measuring time point.

Statistical significance will be defined using two-sided tests with $\alpha=0.05$, unless otherwise specified. All statistical analyses will be performed by Department of Biostatistics using SAS version 9.4 (SAS Institute, Cary, North Carolina).

The primary endpoint of the study is to compare health status change with dapagliflozin versus placebo as measured by KCCQ clinical summary scores (KCCQ CS) at 12 weeks. This will be analyzed using ANCOVA adjusting for baseline KCCQ CS, gender, eGFR, Diabetes status, permanent atrial fibrillation status, and LVEF. Patient participation in the Echocardiography sub-study will not be

controlled for because we don't hypothesize that participation in the Echocardiography sub-study is associated with the outcome (KCCQ CS).

For the primary endpoint a sample size of 145 for each group will achieve 82% power with $\alpha=0.05$ to detect a 4.7 difference in mean KCCQ CS between dapagliflozin group and placebo group at 12 weeks. The assumptions for this calculation was derived from Define-HF study where the adjusted mean difference between dapagliflozin group and placebo group is 4.7 and the standard deviation is 13.7. Assuming a 10% loss to follow up, we arrive at a sample size of ~320 patients.

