12.2 Methods of statistical analyses

Randomization will be stratified by diabetes status (diabetes vs. no-diabetes), permanent atrial fibrillation status (Yes vs. No), and by patients' participation in the echocardiography sub-study.

Baseline demographic and clinical data will be described between treatment and placebo study arms as mean \pm standard deviation for continuous variables and compared using Student's T-test. Whereas discrete variables will be represented as a number and (%) and compared using the χ^2 or Fisher's exact test, as appropriate.

The time course of continuous variables will be presented using standard descriptive summary statistics calculated at each scheduled measuring time point and the last individual measuring time point. Moreover, standard descriptive summary statistics will be calculated for the change (absolute or percent) from baseline to each scheduled measuring time point after baseline and the last individual measuring time point.

Statistical significance will be defined using two-sided tests with $\alpha=0.05$, unless otherwise specified. All statistical analyses will be performed by the Department of Biostatistics using SAS version 9.4 (SAS Institute, Cary, North Carolina).

The primary endpoint of the study is to compare health status change with dapagliflozin versus placebo as measured by KCCQ clinical summary scores (KCCQ CS) at 12 weeks. This will be analyzed using ANCOVA adjusting for baseline KCCQ CS, gender, eGFR, Diabetes status, permanent atrial fibrillation status, and LVEF. Patient participation in the Echocardiography sub-study will not be controlled for because we don't hypothesize that participation in the Echocardiography sub-study is associated with the outcome (KCCQ CS).

For the primary endpoint a sample size of 145 for each group will achieve 82% power with $\alpha=0.05$ to detect a 4.7 difference in mean KCCQ CS between dapagliflozin group and placebo group at 12 weeks. The assumptions for this calculation was derived from Define-HF study where the adjusted mean difference between dapagliflozin group and placebo group is 4.7 and the standard deviation is 13.7. Assuming a 10% loss to follow up, we arrive at a sample size of ~320 patients.

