2.3 Strata, Covariates, and pre-specified subgroup analyses

All efficacy and safety endpoints will be analyzed in the entire cohort, and then within the subgroups of patients with and without diabetes. Analyses for the primary and secondary endpoints will be adjusted for the corresponding baseline measurements as well as sex, eGFR, diabetes (DM), permanent AFib, and LVEF. Restricted cubic splines will be used for continuous variables to accommodate non-linear effects, as appropriate.

A sensitivity analysis will repeat the primary analysis but will also include site as a random effect to account for potential clustering by enrolling centers. Another sensitivity analysis for the primary endpoint will be performed using the imputed KCCQ values as described in section 2.6.

Additionally, the following pre-specified subgroup analyses will be performed for the primary endpoints (stratified by the baseline variables below):

- Baseline NTproBNP (< median, \geq median)
- Baseline LVEF (\leq 60%, $>$ 60%)
- Atrial fibrillation type (No AFib, permanent/persistent AFib, paroxysmal AFib)
- Baseline KCCQ overall summary score (<median, \geq median)
- Baseline eGFR ($<$ 60, \geq 60 mL/min/1.73 m²)
- Age ($<$ 70, \geq 70)
- Sex (male, female)
- Race (white, non white)
- BMI(<median, \geq median)

- Furosemide equivalent mean daily dose: ≤ 40 mg, >40 mg
- NYHA Class (II, III or IV)

Subgroup analyses will be carried out by augmenting the primary analysis model with terms for subgroup and a subgroup-by-treatment interaction. Adjusted point estimates and 95% confidence intervals will be calculated for the effect of dapagliflozin compared with placebo within each subgroup. An interaction p-value will be provided.

Due to the large number of study sites and the expected low number of patients per site, site effects will not be explored, although study site will be included as a random effect in efficacy sensitivity analyses to account for within-site correlations, as specified above.

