2.6 Missing Data

There are three possible sources for missing data:

1. Deaths
2. Administrative error
3. Premature study terminations

Missing data due to deaths is expected to be very low (fewer than 10 patients) because of the short follow-up period. Missing data due to administrative error is believed to be negligible due to the study management procedures and is also believed to be missing completely at random (MCAR). For patients who drop out of the study prematurely, a premature treatment discontinuation visit (PTDV) will be scheduled for them, whenever possible, to get the last assessment. The PTDV assessment will be carried forward to the next follow-up time point. For partially completed KCCQ questionnaires, the scoring algorithm accommodates a limited number of skipped responses. Values that are missing at randomization but available at screening will be imputed using the value at screening. Primary, secondary, and exploratory endpoints will be analyzed among patients for whom all relevant data for the given endpoint can be calculated.

For KCCQ scores, additional sensitivity analysis will be conducted using multiple imputation to account for missing values. IVEware (Raghunathan et al. 2002) will be used to perform the multiple imputation which employs iterative sequential regression to sample missing values from the predictive distribution of each variable, conditional on all other variables included in the imputation model. The following variables will be included in the imputation model: baseline KCCQ scores, sex, baseline eGFR, history of diabetes (DM), history of permanent AFib, baseline LVEF, baseline NYHA class, heart failure hospitalization during the trial duration, urgent heart failure visit during the trial duration, and covariates used as subgroup variables in section 2.3. Additionally, the imputation model will also include all follow up

assessments available for KCCQ scores, eGFR, NTproBNP, BNP, Hgb, loop Diuretic dose, 6-minute walk test.

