6 EFFICACY ANALYSES

6.1 Analysis of the Primary Efficacy Endpoint

Analysis of the primary efficacy endpoints will be performed on the modified ITT data set, first on the entire cohort, then within the subgroups of patients with and without diabetes, and then within other subgroups as specified in section 2.3. Sensitivity analyses will be performed as outlined in section 2.3; in addition, supportive analyses will be repeated using the same models on the on-treatment set (OTS) and per-protocol set (PPS), as applicable.

Mean, standard deviation, median, and interquartile range (IQR) will be reported for KCCQ clinical summary score and for its change at 12-week follow-up, for the entire cohort and by treatment group.

An ACCOVA model will be used to estimate the effect of dapagliflozin on the 12-week KCCQ clinical summary score, adjusting for baseline KCCQ clinical summary score, sex, eGFR, Diabetes status, permanent atrial fibrillation status, and LVEF. Patient participation in the Echocardiography sub-study will not be controlled for because we don't hypothesize that participation in the Echocardiography sub-study is associated with the primary outcome (KCCQ CS).

A sensitivity analysis will repeat the primary analysis but will also include site as a random effect to account for potential clustering by enrolling center. Another sensitivity analysis will be performed using the imputed KCCQ values as described in section 2.6.

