6.2.1 Kansas City Cardiomyopathy Questionnaire (KCCQ) overall summary score at 12 weeks

KCCQ overall summary score at 12 weeks will be analyzed in a manner analogous to that of the primary endpoint.

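### The primary ANCOVA leaves out one of the three randomisation strata, echo-substudy participation; adding it is a minor, nearly free gain in precision

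*SAP*

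**What the plan says.** Protocol 12.2 sets out the allocation: "Randomization will be stratified by diabetes status (diabetes vs. no-diabetes), permanent atrial fibrillation status (Yes vs. No), and by" participation in the echocardiography substudy. Protocol 4 says the same. Appendix C adds that the third stratum is there to balance the arms within the substudy.

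The primary ANCOVA uses baseline KCCQ clinical summary score, sex, eGFR, diabetes, permanent AF and LVEF. SAP 2.3 applies one covariate list to all primary and secondary endpoints, which "will be adjusted for the corresponding baseline measurements as well as sex, eGFR, diabetes (DM), permanent AFib, and LVEF". Echo participation is absent from both.

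The omission is deliberate and consistent. SAP 6.1 says "Patient participation in the Echocardiography sub-study will not be controlled for because we" have no hypothesis linking it to the primary outcome. The Protocol synopsis ("Patient participation in the Echocardiography sub-study will not be" controlled for), Protocol 12.2 and Protocol 12.2.1 give the same reason. No data or citation is offered.

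The other planned analyses inherit the omission:
- **Subgroups (SAP 2.3):** "Subgroup analyses will be carried out by augmenting the primary analysis model with terms for subgroup and a subgroup-by-treatment interaction". Echo participation is not on the subgroup list.
- **On-treatment and per-protocol sets (SAP 6.1):** "supportive analyses will be repeated using the same models on the on-treatment set (OTS) and per-protocol set (PPS), as applicable".
- **Site sensitivity analysis (SAP 2.3, 6.1):** adds site as a random effect and nothing else.
- **Multiple imputation (SAP 2.6):** the variable list ("The following variables will be included in the imputation model: baseline KCCQ scores, sex, baseline eGFR, history of diabetes (DM), history of permanent AFib" and others) does not name participation.
- **KCCQ overall summary score (SAP 6.2.1):** "KCCQ overall summary score at 12 weeks will be analyzed in a manner analogous to that of the primary endpoint". The six-minute walk (SAP 6.2.4) is handled the same way.

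**The concern.** Stratified allocation forces the arms to be balanced on echo participation. If participation is related to outcome, that balance makes the treatment estimate less variable. The ANCOVA's standard error reflects the gain only when the factor is in the model. Otherwise the variation between participants and non-participants stays in the residual, and the interval is wider than the design warrants.

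Having no hypothesis of an association is not evidence that there is none. Substudy entry is also selective: Protocol 4.2 (criteria 29 and 30) bars permanent AF, ventricular paced rhythm and left bundle branch block, and of these only permanent AF is a covariate. What is at stake is a little precision on the primary comparison.

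**Working it through.** **Inputs.** 145 evaluable per arm, difference 4.7, SD 13.7, two-sided alpha 0.05 (SAP 1.3, 2.5). About 320 randomised (SAP 1.3), 130 of them in the echo substudy (Protocol Appendix C). Permanent AF may be capped at 33% (Protocol 4) and is barred from the substudy.

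**The plan's own figure.** SE = 13.7 × √(2/145) = 1.609. Power = Φ(4.7/1.609 − 1.96) = 83.2%, or 82.9% with the noncentral t. The stated 82% is reproduced, and it does not depend on the echo term.

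**Assumptions.** The documents do not give the gap g in 12-week score between participants and non-participants that remains after adjustment, so 2, 3 and 5 points are assumed. The SD of 13.7 is taken as the residual SD of the model without the echo term.

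**Variance of participation, v.**
- Upper end, no credit for AF already being in the model: p = 130/320 = 0.406, so v = 0.406 × 0.594 = 0.241.
- Lower end, AF at its cap: 0.67 × 320 = 214.4 patients without permanent AF, q = 130/214.4 = 0.606, so v = 0.67 × 0.606 × 0.394 = 0.160.

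**Formulas.** R² = v·g²/13.7² and f = √(1 − R²). Under stratified randomisation the true SE is 1.609·f, while the model without the term reports about 1.609. Hence:
- SE excess = 1/f − 1
- type I error without the term = 2(1 − Φ(1.96/f))
- power without = Φ((4.7 − 1.96 × 1.609)/(1.609·f))
- power with = Φ(4.7/(1.609·f) − 1.96)

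**Worked case, g = 5, upper v.** R² = 0.241 × 25/187.69 = 0.032; f = 0.984; true SE = 1.583. SE excess is 1.6% and type I error 4.6%. Power is Φ(0.977) = 83.6% without the term and Φ(1.009) = 84.4% with it.

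| Assumed gap | R² | SE excess | Type I error without | Power without | Power with | Gain (points) |
|---|---|---|---|---|---|---|
| 0 | 0 | 0 | 5.0% | 83.2% | 83.2% | 0 |
| 2 | 0.003–0.005 | 0.2–0.3% | 4.9–5.0% | 83.2% | 83.3–83.4% | 0.1 |
| 3 | 0.008–0.012 | 0.4–0.6% | 4.9% | 83.3% | 83.5–83.6% | 0.2–0.3 |
| 5 | 0.021–0.032 | 1.1–1.6% | 4.6–4.8% | 83.4–83.6% | 84.0–84.4% | 0.5–0.8 |

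At 5 points the 95% half-width falls from 3.15 to 3.10–3.12.

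**Simulation check.** N = 290, 33% AF, 40% diabetes, blocks of 4 within strata (block size assumed), 6,000 runs per case. At a 5-point gap, type I error was 4.6% without and 4.8% with the term, and power 83.3% and 83.8%. The mean estimates from the two models differed by less than 0.001 points, which confirms that omission does not bias the effect.

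**Cost if there is no gap.** With linear terms the model has 8 parameters, so residual df go from 290 − 8 = 282 to 281. The critical value rises by about 0.002%, and the SE by at most √(282/281) − 1 = 0.2%.

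**The case against.** The case for leaving the plan alone is reasonable. The choice is pre-specified, disclosed and the same everywhere, so the analyst knows exactly what to fit. Leaving out a variable that is not expected to matter is an ordinary prior judgement. The stratum was introduced to protect the substudy comparison and was not chosen as a predictor of KCCQ. Permanent AF, one of the two entry limits set by rhythm or conduction, is already in the model. If the other, paced rhythm or left bundle branch block, were the only source of a gap, and one assumes 5 to 30% of non-participants have it and score 5 to 10 points lower, the gap is 0.05 × 5 = 0.25 to 0.30 × 10 = 3 points and the SE excess stays below 0.6%. Power never falls below the planned figure. The Protocol edits amount to an amendment under Protocol 9.5, and a single sensitivity analysis in the SAP would be a smaller change.

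Most of this stands, and it keeps the point minor. It does not remove it. Whatever the stratum's purpose, it constrains the whole-cohort allocation, and the model SE is too large whenever the factor is prognostic. A sensitivity analysis would test the assumption but leave the primary interval as it is.

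A reader might infer from the selective substudy entry that participation does predict KCCQ. The documents contain no data on that. Gaps well above 5 points, with correspondingly larger losses, would be hypothetical: the gap has to survive adjustment for the baseline score and five other covariates.

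**Conclusion.** The point holds as a minor, nearly free improvement. One of three randomisation strata is missing from the primary model and from the common covariate list, and no planned analysis includes it. If participation is prognostic after adjustment, the reported SE is too large by about 0.2 to 0.6% at an assumed 2 to 3 points and 1.1 to 1.6% at an assumed 5 points. The matching power gains are at most 0.3 and 0.5 to 0.8 percentage points. If it is not prognostic, nothing material is lost by including it.

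These figures rest on the assumed gap, on 130 of 320 patients joining the substudy, and on 13.7 as the residual SD. A reader might conclude that omitting a stratification factor invalidates the primary test, inflates its error rate or leaves the trial underpowered. None of these follows: the estimate is unbiased, any effect on type I error is downward, and the stated 82% power is met without the term.

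**What to change.** Before unblinding:
- **SAP 6.1:** add echo-substudy participation (yes/no, as randomised) as a main effect in the primary ANCOVA and delete the sentence excluding it.
- **Protocol synopsis, 12.2 and 12.2.1:** delete the same sentence at the next amendment.
- **SAP 2.3:** add the term to the covariate list, so that the primary and secondary models that use the list stay consistent. SAP 6.2.2 and 6.2.6 spell the list out and need the matching edit. The subgroup, site, on-treatment and per-protocol analyses then follow from their existing wording.
- **SAP 2.6:** add participation to the imputation model, so that the analysis model holds no covariate the imputation model lacks.
- **SAP 6.3.8:** state that the term is dropped for echo endpoints, where it is constant.

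The statistical cost is one degree of freedom of about 280. No patients are lost: participation is known at randomisation, so it creates no new exclusions under SAP 10.2 item 6.8 (missing covariates). The administrative cost is the SAP edits and three deletions carried in a Protocol amendment.

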6.2 Secondary outcome variables

The following secondary outcomes will be analyzed on the intention to treat (modified ITT) data set, first on entire patient cohort and then within subgroups of patient with or without diabetes.

6.2.1 Kansas City Cardiomyopathy Questionnaire (KCCQ) overall summary score at 12 weeks

KCCQ overall summary score at 12 weeks will be analyzed in a manner analogous to that of the primary endpoint.

6.2.3 BNP at 6 and 12 weeks

BNP at 6 and 12 weeks will be analyzed in a manner analogous to that of NT pro-BNP.

6.2.4 Six-minute walk test at 12 weeks

Six-minute walk test at 12 weeks will be analyzed in a manner analogous to that of the primary endpoint.

6.2.5 HbA1c at 6 and 12 weeks

HbA1c at 6 and 12 weeks will be analyzed in a manner analogous to that of NT pro-BNP, although appropriate distributions and link functions will be chosen for the given outcomes. Models will also provide separate effect estimates for the 6- and 12-week time points

6.2.6 Proportion of patients with a \geq 5pts increase in KCCQ clinical summary score and KCCQ overall summary score at 12 weeks

Proportion of patients achieving a \geq 5pts increase in KCCQ clinical summary score at 12 weeks

Unadjusted proportion of patients achieving a \geq 5pts increase in KCCQ clinical summary score at 12 weeks, will be reported for the treatment group and placebo group. A logistic regression model will be used to assess the treatment effect. Model will be adjusted for baseline measurement, sex, eGFR, diabetes (DM), permanent AFib, and LVEF. Several sensitivity analyses will be performed:

- Repeat the model above but also include site as a random effect to account for potential clustering by enrolling center.
- Repeat the model above on the on-treatment set (OTS).
- Repeat the model above excluding patients with baseline KCCQ clinical summary score of over 90 (as these patients will have a limited opportunity for improvement in KCCQ)
- Repeat the analysis using the imputed KCCQ values as described in section 2.6.

Proportion of patients achieving a \geq 5pts increase in KCCQ overall summary score at 12 weeks

Proportion of patients achieving a \geq 5pts increase in KCCQ overall summary score at 12 weeks will be analyzed in a manner analogous to that of proportion of patients achieving a \geq 5pts increase in KCCQ clinical summary score at 12 weeks.

6.2.7 Proportions of patients with a \geq 20% decrease at 6 and 12 weeks NTproBNP

This end point will be analyzed in a manner analogous to 6.2.6.

6.2.8 Proportions of patients with a \geq 5pts increase in KCCQ and a \geq 20% decrease in 6 and 12 weeks NTproBNP

This end point will be analyzed in a manner analogous to 6.2.6. Proportion will be calculated for patients with a \geq 5 pts increase in KCCQ and a \geq 20% decrease in NTproBNP at 6 weeks, and separately for patients with a \geq 5 pts increase in KCCQ and a \geq 20% decrease in NTproBNP at 12 weeks.

6.2.9 Weight at 6 and 12 weeks

Weight at 6 and 12 weeks will be analyzed in a manner analogous to that of NT pro-BNP, although appropriate distributions and link functions will be chosen for the given outcomes. Models will also provide separate effect estimates for the 6- and 12-week time points

6.2.10 Systolic blood pressure at 6 and 12 weeks

Systolic blood pressure at 6 and 12 weeks will be analyzed in a manner analogous to that of NT pro-BNP, although appropriate distributions and link functions will be chosen for the given outcomes. Models will also provide separate effect estimates for the 6- and 12-week time points

6.3 Exploratory outcome variables

6.3.1 Composite mean hierarchical-rank clinical score.

The composite hierarchical-rank clinical score will be analyzed on the safety dataset. Patients with missing KCCQ values at 12 weeks will be excluded unless they died or had HF hospitalizations or urgent HF visits. Win ratio will be used to compare the rank score of each patient in the dapagliflozin arm with each patient in the placebo group. Each comparison will result in a “win”, “loss” or “tie” for the patient in the dapagliflozin group if the analysis value of the patient in the dapagliflozin group is higher, lower or equal to the analysis value of the patient in the placebo group, respectively. Within the dapagliflozin group, total number of wins will be divided by the total number of losses (ties are split evenly between wins and losses) to form the Win Ratio statistic of the dapagliflozin group against the placebo group (Pocock et al 2012). The confidence interval of the win ratio statistic will be calculated as described in Gasparyan et al 2020 (see APPENDIX).

6.3.2 Heart failure hospitalizations

Number of heart failure hospitalizations and proportion of patients with any heart failure hospitalizations during the length of follow-up will be summarized descriptively for the treatment and placebo group on the safety dataset. This will be completed first on the entire cohort and then within subgroups of patients with or without diabetes. Both endpoints will be summarized by frequency and percent and compared using χ^2 or Fisher’s exact tests, as appropriate.

In addition, a Cox proportional hazard model will be used to assess the effect of treatment vs. placebo on the time to the first occurrence of heart failure hospitalization, adjusting for sex, eGFR, diabetes (DM), permanent AFib, and LVEF. A second sensitivity analysis will be performed using stratified Cox proportional model conditional on site to account for clustering.

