1.3 Sample Size and Power

Planned Sample Size	Approximately 160 patients will be enrolled in each arm.
Power Statement	For the primary endpoint a sample size of 145 for each group will achieve 82% power with $\alpha=0.05$ to detect a 4.7 difference in mean KCCQ CS between dapagliflozin group and placebo group at 12 weeks. The assumptions for this calculation was derived from DEFINE-HF trial where the adjusted mean difference between dapagliflozin group and placebo group is 4.7 and the standard deviation is 13.7. Assuming a 10% loss to follow up, we arrive at a sample size of ~320 patients.

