4.3 Exploratory Outcome Variables

- Composite mean hierarchical-rank clinical score.

All patients will receive a global rank endpoint based on time to death (tier 1), time to HF hospitalization or urgent HF visit (tier 2), or change in KCCQ clinical summary score from baseline to 12 weeks. The variable for ranking the patients will be derived as follows.

- Patients dying during the study will have a value of $0 + (\text{study days from randomization to death})$. Patients with missing vital status at the end of trial will be excluded from the analysis. Patient dying during the study but with no mortality date will use the average of the last known alive date and the patient's scheduled 12 weeks follow-up date.

- Patients who did not die but had multiple occurrences of HF hospitalization or urgent HF visit will have a value of 200 – number of occurrences.
- Patients who did not die but have only one HF hospitalization or urgent HF visit will have a value of 200 + (study days from randomization to the occurrence of HF hospitalization or urgent HF visit). Patients known to have an event but event date is unknown will be imputed using the median rank based on the rank of other patients in this category.
- Patients who did not die and did not experience HF hospitalization or urgent HF visit will have a value of 400 + (change in KCCQ clinical summary score from baseline to week 12).

Patients with missing KCCQ at 12 weeks who didn't die and didn't have HF events will be excluded. A sensitivity analysis will be performed where these patients will be kept in the analysis and the KCCQ values will be imputed using multiple imputation as described in section 2.6.

- Number of heart failure hospitalizations and proportion of patients experienced heart failure hospitalizations
- Number of urgent heart failure visits and proportion of patients with urgent heart failure visits
- Total number of heart failure hospitalizations and urgent heart failure visits and proportion of participants who experienced any heart failure hospitalizations and urgent heart failure visits.

For the four endpoints above, only events positively adjudicated by the clinical event committee will be included. Events that occurred between screening and randomization, and between 12 weeks and 13 weeks will be excluded from this analysis. Events that occurred between the week 12 and week 13 study visits will be reported in a separate, supplemental analysis.

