6.3.3 Urgent heart failure visits

Will be analyzed in a manner analogous to that described in 6.3.2.

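### SAP 6.3.2 applies chi-square/Fisher to the number of HF events as well as to the proportion of patients; if event totals are tested, repeat events count as independent and the p-value can be too small (exploratory endpoints only)

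*SAP*

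**What the plan says.** SAP 6.3.2 opens with "Number of heart failure hospitalizations and proportion of patients with any heart failure hospitalizations during the length of follow-up will be summarized descriptively" by arm. It goes on: "Both endpoints will be summarized by frequency and percent and compared using" chi-square or Fisher's exact test, as appropriate. So the section first calls the summary descriptive and then plans a test, and the test covers both the count and the proportion.

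SAP 6.3.3 (urgent visits) says "Will be analyzed in a manner analogous to that described in 6.3.2", and 6.3.4 (the combination) does the same. SAP 4.3 defines the combined endpoint as "Total number of heart failure hospitalizations and urgent heart failure visits and proportion of participants who experienced any" event, which keeps the total apart from the proportion. The ranking rule in the same section provides for "Patients who did not die but had multiple occurrences of HF hospitalization or urgent HF visit", so repeats are foreseen.

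In Protocol 2.3 and 12.2.3, exploratory outcomes 2 to 4 are all numbers of events. The proportion and the Cox model appear only in the SAP. The Cox model uses the first event only. Its site-stratified version deals with clustering by site, not with repeats within a patient.

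**The concern.** A 2x2 chi-square or Fisher test needs independent units, each contributing at most one event. Patients with or without any event meet that condition. A total of events set against a number of patients does not, because one patient can contribute several events and those events are correlated. The binomial variance is then smaller than the true variance of the total, and a null difference reaches nominal significance too often.

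No other planned analysis tests the count on its own. The Cox model drops repeats, and the win ratio ranks a composite. For three count endpoints named in the protocol, the only p-value could therefore be an anticonservative one, with no multiplicity control (SAP 2.5).

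**Working it through.** **Inputs from the documents.** SAP 1.3: "Approximately 160 patients will be enrolled in each arm". Protocol 12.2: "Statistical significance will be defined using two-sided tests with" alpha 0.05. The plan states no rate, power or error figure for HF events, so only its sample size can be reproduced. With 145 per group, difference 4.7 and SD 13.7, power = Phi(4.7/(13.7 x sqrt(2/145)) - 1.96) = Phi(0.96) = 0.832 (0.829 with the t distribution), against 82% stated. Allowing 10% loss, 290/0.9 gives 323 (290 x 1.1 = 319), against about 320 stated. The 160 per arm used below is therefore sound.

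**Assumptions, not in the documents.** Mean HF events per patient over 12 weeks: 0.05, 0.10 or 0.15. Between-patient variation: none (Poisson), or gamma frailty with shape 0.5, 0.25 or 0.1. The variance-to-mean ratio is VMR = 1 + mean/shape. At shape 0.1 this gives 1 + 0.05/0.1 = 1.5, 1 + 0.10/0.1 = 2.0 and 1 + 0.15/0.1 = 2.5.

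**Formula.** The chi-square test assumes a per-patient variance of rate x (1 - rate). The true variance is rate x VMR. Hence actual alpha = 2 x [1 - Phi(1.96 x sqrt((1 - rate)/VMR))].

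- Rate 0.05, VMR 1: 1.96 x sqrt(0.95) = 1.91, alpha 0.056.
- Rate 0.10, VMR 2: 1.96 x sqrt(0.45) = 1.31, alpha 0.189.
- Rate 0.15, VMR 2.5: 1.96 x sqrt(0.34) = 1.14, alpha 0.253.

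**Simulation, chi-square.** Total events against patients, no treatment effect, 160 per arm, 8,000 trials per cell, nominal 5%:

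| Mean events per patient | No variation | Shape 0.5 | Shape 0.25 | Shape 0.1 |
|---|---|---|---|---|
| 0.05 | 5.5% | 6.6% | 7.9% | 11.3% |
| 0.10 | 5.8% | 8.4% | 12.5% | 18.9% |
| 0.15 | 7.2% | 11.1% | 15.0% | 24.9% |

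A second run with 20,000 trials per cell gave 5.3% to 24.8% on the same grid.

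**Simulation, Fisher** (20,000 trials per cell). At mean 0.05: 2.8%, 3.9%, 4.3% and 7.3% across the four columns. With no variation: 4.2% at mean 0.10 and 5.3% at mean 0.15. The highest cell on the grid is 21.5%. Fisher's conservatism offsets the problem when events and repeats are few, but not otherwise.

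**Per-patient comparisons.** On the same grid, the difference in mean events per patient with between-patient (robust) variance holds 4.4-5.3%. Over a wider grid (rates 0.05 to 0.30, VMR 1 to 2.5), chi-square on patients classed as 0, 1 or 2+ events gives 3.1-5.2%.

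**Sparsity.** Expected events over 320 patients are 320 x 0.05 = 16 to 320 x 0.15 = 48. The planned diabetes stratum of about 128 would have 128 x 0.05 = 6.4 at the lowest rate.

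**The case against.** The SAP may intend a per-patient table. Section 5 uses almost the same sentence for categorical patient variables, and 6.3.7 names the same tests for NYHA categories. A percent makes sense for patients with 0, 1 or 2+ hospitalisations, whereas an event total has no stated denominator. On that reading each patient is counted once and the test is valid. This stands as a possibility. Against it, the SAP sets the number apart from the proportion, calls the combined endpoint a total, and nowhere describes such a table. The text needs an edit on either reading.

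The size is also open. At shape 0.1, about 19-37% of patients with any event would have a repeat within 12 weeks, which is the heavy end of the assumptions. With no between-patient variation chi-square reaches only 5.5-7.2%, and Fisher stays below 5% at mean 0.05 unless repeats are heavy. A reader might infer that the p-value will certainly be too small. The documents do not support that, because they fix neither the rate, nor the repetition, nor which of the two tests will be used.

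Finally, these endpoints are exploratory, and the same section plans two analyses without this fault. Repeats also enter the hierarchical score, though that does not test the count. All of this stands and limits the weight of the point.

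**Conclusion.** The point holds conditionally and is minor. As written, the chi-square/Fisher rule extends to event counts in SAP 6.3.2 to 6.3.4. If totals are tested against patients, type I error at a nominal 5% is about 5-25% with chi-square and 3-22% with Fisher. Those ranges rest on the assumed 0.05 to 0.15 events per patient and on frailty from none to shape 0.1. Where repeats are rare, inflation is small or absent.

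A reader might go further and conclude that the trial's clinical-event evidence as a whole is compromised. The documents do not support that. Only the exploratory count comparisons are affected. The proportion with any event, the time-to-first-event Cox model, the primary KCCQ result, the sample size and the primary alpha are untouched.

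**What to change.** In SAP 6.3.2, and by reference in 6.3.3 and 6.3.4:

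- Keep chi-square/Fisher for the proportion of patients with any event.
- Compare event counts by a rate ratio with 95% confidence interval, from a Poisson model with robust patient-level variance or a negative binomial model. Use log follow-up time as offset; follow-up can differ through death, withdrawal, or the delayed Week 12 visits that Protocol Appendix D allows.
- Include treatment only, or very few covariates. With perhaps 16 to 48 events, the five covariates of the Cox model are likely too many.
- Where events are too few to model, for example within the diabetes subgroups, report counts by arm without a p-value.
- If a table of patients by number of events was meant, say so and give the categories; chi-square/Fisher can then stay.

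The cost is a sentence or two in the SAP and a few lines of code, with no new data. If made before unblinding, the change introduces no bias. The downsides are somewhat wider uncertainty for the counts and possible non-convergence with very few events, so the descriptive fallback should be written in advance.
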